## **Study Site and Subjects (Source, Inclusion, and Exclusion Criteria)**

All patients in this study will be inpatients from the Department of Gastrointestinal Surgery, Qilu Hospital.

### **Inclusion Criteria:**

Patients preoperatively diagnosed with resectable gastric cancer.

Patients without distant organ metastasis.

Patients with preoperative OCST or PSG results showing AHI >30 events/hour and SaO2 <80%.

Patients with cardiopulmonary function deemed suitable for surgery.

Patients aged 18-85 years.

Patients who voluntarily joined this study and provided written informed consent.

### **Exclusion Criteria:**

Patients with a history of or concurrent other malignant tumors.

Patients who underwent palliative resection.

Subjects who experienced acute cardiovascular or cerebrovascular events (e.g., acute cerebral infarction, acute coronary syndrome) within the past 3 months, or whose cardiovascular clinical symptoms/diseases are not well-controlled.

Patients with a history of psychotropic drug abuse that cannot be abstained, or those with psychiatric disorders.

Patients with concomitant diseases that, in the investigator's judgment, seriously endanger the patient's safety or affect the completion of the study.

## **Study Variables (Factors) and Measurement**

Study Variable: Whether endotracheal extubation time is prolonged.

## **Study Outcomes**

Incidence of short-term postoperative complications, graded using the Clavien-Dindo classification.

## **Follow-up (For Cohort Studies)**

Routine follow-up examinations at 1, 3, 6, 9, and 12 months postoperatively. Collect routine follow-up indicators and assess the occurrence of postoperative complications.

## **Sample Size**

The incidence of postoperative complications in gastric cancer patients with severe sleep apnea is the primary endpoint of this study. Based on previous large-scale literature reports, the incidence of perioperative cardiovascular complications in patients with severe sleep apnea undergoing non-cardiac surgery is 15% higher than in the normal population [8]. Using a power of 90% and a significance level of 5%, sample size estimation was performed using PASS, version 11 (NCSS, LLC). We need to recruit 93 patients per group. Accounting for loss to follow-up, dropouts, and other factors, we plan to include 120 patients per group, totaling an estimated 240 patients for both groups.

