### **Study Abstract**

Item	Content
Project Title	An Exploratory Study on the Impact of Prolonged Postoperative Endotracheal Extubation Time on Postoperative Complications in Gastric Cancer Patients with Severe Obstructive Sleep Apnea
Study Objective	To investigate the impact of prolonging the time to postoperative endotracheal extubation on the incidence of postoperative complications in gastric cancer patients with severe obstructive sleep apnea.
Research Hypothesis	Prolonging the time to endotracheal extubation in gastric cancer patients with severe obstructive sleep apnea can reduce the incidence of postoperative complications.
Study Design	 Case-Control Study  Cohort Study 

Item	Content
Cross-Sectional Study	
	 Case Report / Case Series
Inclusion Criteria:	
 
1. Patients preoperatively diagnosed with resectable gastric cancer.
 
2. Patients without distant organ metastasis.
 
3. Patients with preoperative OCST or PSG results showing AHI >30 events/hour and Sa02 <80%.
 
4. Patients with cardiopulmonary function deemed suitable for surgery.
 
5. Patients aged 18–85 years.
 
6. Patients who voluntarily joined this study and provided written informed consent.
 

Exclusion Criteria:	
 
1. Patients with a history of or concurrent other malignant tumors.
 
2. Patients who underwent palliative resection.
 
3. Subjects who experienced acute cardiovascular or cerebrovascular events (e.g., acute cerebral infarction, acute coronary syndrome) within the past 3 months, or whose cardiovascular clinical symptoms/diseases are not well-controlled.
 
4. Patients with a history of psychotropic drug abuse that cannot be abstained, or those with psychiatric disorders.
 
5. Patients with concomitant diseases that, in the investigator's judgment, seriously endanger the patient's safety or affect the completion of the study.
 

Meet either (A + B) or C below.	

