	
A: Presence of at least 1 of the following: (1) Patient complaints of sleepiness, non-restorative sleep, fatigue, or insomnia; (2) Waking from sleep due to choking or gasping; (3) Bed partner or other observer reports of habitual snoring, breathing interruptions, or both during sleep; (4) Diagnosed hypertension, mood disorder, cognitive dysfunction, coronary artery disease, cerebrovascular disease, congestive heart failure, atrial fibrillation, or type 2 diabetes.
 
B: PSG or OCST confirms <math>\geq 5</math> respiratory events/hour during monitoring, including obstructive apneas,

Item	Content
Sample Size & Justification	
mixed apneas, hypopneas, and respiratory effort-related arousals (RERAs).
 
C: PSG or OCST confirms <math>\geq 15</math> respiratory events/hour during monitoring, including obstructive apneas, mixed apneas, hypopneas, and RERAs.

Primary Exposure Factor	
The incidence of postoperative complications in gastric cancer patients with severe sleep apnea is the primary endpoint of this study. Based on previous large-scale literature reports, the incidence of perioperative cardiovascular complications in patients with severe sleep apnea undergoing non-cardiac surgery is 15% higher than in the normal population [8]. Using a power of 90% and a significance level of 5%, sample size estimation was performed using PASS, version 11 (NCSS, LLC). We need to recruit 93 patients per group. Accounting for loss to follow-up, dropouts, and other factors, we plan to include at least 120 patients per group.

Outcome Variables	
Time to endotracheal extubation

Follow-up Plan (For Cohort Studies)	
Incidence of short-term postoperative complications, graded using the Clavien-Dindo classification.
 
Routine follow-up examinations at 1, 3, 6, 9, and 12 months postoperatively. Collect routine follow-up indicators and assess the occurrence of postoperative complications.

Sample Collection	
 No  Yes
 
Brief description of tissue type and quantity: N/A

Non-Medical Purpose Examinations	
 No  Yes
 
e.g., unnecessary CT scans, contrast studies, lab tests, etc.: N/A

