**Confidentiality Statement:**

The information contained in this study protocol is provided solely to the investigators of this project, the clinical research management committee, and relevant regulatory bodies for review. Disclosing any information to third parties unrelated to this study is strictly prohibited without the approval of the Principal Investigator.

**1. Research Background (State the rationale and significance of this study based on current domestic and international research)**

As one of the most common malignant tumors worldwide, gastric cancer ranks fifth in global cancer incidence and fourth in cancer mortality [1]. Current treatment for gastric cancer is comprehensive, primarily based on surgical treatment, with standard radical gastrectomy being the main procedure [2]. This process is complex, technically demanding, and carries relatively high surgical risks. Obstructive Sleep Apnea (OSA) is a sleep-related breathing disorder characterized by periodic partial or complete upper airway obstruction during sleep, manifesting as apneas and hypopneas [3]. Preliminary statistics indicate the overall prevalence of OSA among adults in China is 3.93% [4], yet the clinical diagnosis rate remains low. OSA is widely recognized as an independent risk factor for hypertension and metabolic syndrome [5, 6]. Reported prevalence of OSA among surgical patients is approximately 7%-10%, but can reach 68%-70% in high-risk populations (bariatric surgery or other major non-cardiac surgery). These patients have significantly increased perioperative complications and mortality [7, 8], especially severe sleep apnea. One cohort study reported the incidence of cardiovascular complications within 30 days after surgery in patients with severe sleep apnea was as high as 30.1% [8]. General anesthesia, sedatives, and postoperative analgesics are potent respiratory depressants; they can relax the upper airway dilator muscles and impair the ventilatory response to hypoxemia and hypercapnia. These effects exacerbate OSA. Concurrently, the hypoxemia caused by OSA can increase the incidence of postoperative complications in gastric cancer patients and may predispose them to postoperative cardiovascular complications [9]. Therefore, for gastric cancer patients with severe sleep apnea, strategies to reduce postoperative complications and adverse events are particularly important.

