**2. Research Question & Objectives (Elucidate the scientific question and research objectives)**

To investigate the impact of prolonging the time to postoperative endotracheal extubation on the incidence of postoperative complications in gastric cancer patients with severe obstructive sleep apnea.

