**3. Research Methods (This section should be elaborated in detail)**

## **Study Design**

This is a single-center, prospective cohort study. Starting June 2025, the study plans to enroll patients undergoing radical gastrectomy for gastric cancer in the Department of General Surgery of our hospital who also have severe obstructive sleep apnea. Based on the anesthesiologist's assessment during the perioperative period regarding sufficient metabolism of anesthetic agents and full patient awakening, patients will be divided into two groups regarding whether extubation time is prolonged (by 1-2 days): Exposure Group: Prolonged extubation time group; Non-Exposure Group: Non-prolonged extubation time group (extubation on the day of surgery group). Clinical data, intraoperative details, postoperative pathology, lymph node status, and postoperative complications will be recorded for all patients.

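### The 90% power claim uses a severe-apnea-versus-normal difference in cardiovascular events, not the extubation comparison on all complications that the study makes

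*Protocol*

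**What the plan says.** The Study Abstract gives the hypothesis: "Prolonging the time to endotracheal extubation in gastric cancer patients with severe obstructive sleep apnea can reduce the incidence of postoperative complications". Section 2 gives the objective as "the impact of prolonging the time to postoperative endotracheal extubation on the incidence of postoperative complications". Under Study Design, "patients will be divided into two groups regarding whether extubation time is prolonged (by 1-2 days", and the arms are "Exposure Group: Prolonged extubation time group; Non-Exposure Group: Non-prolonged extubation time group", the latter being patients extubated on the day of surgery. The Inclusion Criteria require an AHI above 30 events/hour of everyone, so both arms have severe apnea and there is no normal-population arm.

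Study Outcomes defines the outcome as short-term postoperative complications graded by Clavien-Dindo. Data Collection and Management lists pulmonary, gastrointestinal and anastomotic events, with cardiovascular and cerebrovascular events added at the end.

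The Sample Size section opens consistently with this: "The incidence of postoperative complications in gastric cancer patients with severe sleep apnea is the primary endpoint of this study". Its only effect-size input follows: "the incidence of perioperative cardiovascular complications in patients with severe sleep apnea undergoing non-cardiac surgery is 15% higher than in the normal population". With 90% power, a 5% significance level and PASS version 11, it arrives at 93 per group, raised to 120 per group (240 in total) for losses. The Study Abstract repeats the justification: "is 15% higher than in the normal population [8]. Using a power of 90% and a significance level of 5" per cent.

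The only event rate for severe apnea in the protocol stands in Research Background, from the same reference: "the incidence of cardiovascular complications within 30 days after surgery in patients with severe sleep apnea was as high as 30.1" per cent. The Sample Size section does not say that it used this rate.

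**The concern.** A power statement holds for one contrast on one endpoint. This one describes people with severe apnea against people without it, on cardiovascular events. The study asks whether extubation timing changes all complications among people who all have severe apnea. A disease-versus-no-disease gap says nothing by itself about how much a change in extubation timing achieves. Using it that way assumes that prolongation removes the whole apnea excess, and that a cardiovascular gap carries over to a composite made up largely of surgical and pulmonary events. The protocol states neither assumption.

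What is at stake is how the result is read. If the groups do not differ significantly, a reader will take it as a negative finding from a study with 90% power on extubation timing. Nothing in the protocol supports that reading.

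**Working it through.** **Inputs from the protocol.** Power 90%, significance level 5%, 93 per group evaluable, 120 per group planned, and a difference described as 15% (Sample Size); 30.1% for cardiovascular events in severe apnea (Research Background).

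**Assumptions made here.** Two-sided test, equal groups, pooled-variance two-proportion formula, and 15% read as absolute percentage points. The protocol states none of these four except the equal groups.

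**Formulae.** With p̄ = (p1 + p2)/2:

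- n per group = [1.960·√(2p̄(1−p̄)) + 1.282·√(p1(1−p1) + p2(1−p2))]² / (p1−p2)²
- power = Φ{ [|p1−p2| − 1.960·√(2p̄(1−p̄)/n)] / √([p1(1−p1) + p2(1−p2)]/n) }

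**Step 1: try to reproduce 93.** With 30.1% vs 15.1%, p̄ = 0.226:

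- n = [1.960 × 0.5915 + 1.282 × 0.5819]² / 0.15² = 161.3, so 162 per group.
- One-sided 5% gives 132 per group. Reading 15% as relative gives roughly 2,070 to 2,755 per group.

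None of these is 93. Solving backwards for a 15-point gap at 90% power, 93 per group comes from:

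| Method | Rates that give 93 |
|---|---|
| Pooled, two-sided | about 19% vs 4% (n = 92.96) |
| Unpooled, two-sided | about 19.4% vs 4.4% |
| Continuity-corrected, two-sided | about 17.2% vs 2.2% |
| Arcsine, two-sided | 20% vs 5% (n = 92.6) |
| Pooled, one-sided | about 22% vs 7% |

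All need a base rate near 17% to 22%, and no such rate appears in the protocol. So 93 cannot be reproduced from the figures given. It is not proven to be an arithmetic error, because the base rate, method and sidedness are unstated.

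**Step 2: power for 30.1% vs 15.1%.** This pairing is mine, not the protocol's, and 30.1% is a cardiovascular rate.

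- n = 93: (0.15 − 1.960 × 0.06133)/0.06034 = 0.494, power 68.9% (exact chi-square 69.6%).
- n = 120: (0.15 − 1.960 × 0.05399)/0.05312 = 0.832, power 79.7% (exact chi-square 80.4%).

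**Step 3: range over assumed all-complication rates.** The protocol gives no such rate for day-of-surgery extubation, so the base is varied (two-sided, pooled).

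| Assumed base rate | Power for a 15-point drop, 93 / 120 per group | Drop detectable at 90% power, 93 / 120 per group |
|---|---|---|
| 20% | 88 / 94% | 15.4 / 14.0 points |
| 30% | 69 / 80% | 19.0 / 17.0 points |
| 40% | 59 / 70% | 21.4 / 19.1 points |
| 50% | 54 / 65% | 22.9 / 20.3 points |

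**Step 4: unequal groups.** Groups form by clinical decision, so an equal split is not assured. With 240 patients split 2:1 in either direction, the detectable drops become about 14.4–14.8, 17.7–18.0, 20.0–20.2 and 21.4–21.5 points from bases of 20%, 30%, 40% and 50%.

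**The case against.** The best defence is that the sponsor borrowed 15 points as a plausible difference to detect, on the idea that prolongation offsets the apnea excess, and entered a base near 20% in PASS. Using the arcsine formula, 20% vs 5% needs 92.6, hence 93 per group, and those are natural round planning rates. The arithmetic may therefore be sound for the rates entered. The 30.1% rate comes from the background section and was probably not the planning input, so the 69% and 80% figures are not the plan's own.

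Sidedness also matters. The hypothesis is directional, and one-sided power for 30.1% vs 15.1% would be 79% at 93 and 88% at 120 per group; from a 20% base it would be 93% and 97%. Finally, the title calls the study exploratory, and a 2:1 split changes the detectable reduction only modestly.

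Most of this stands as a limit on the size of the problem. It rules out saying that 93 is miscalculated or that the study is shown to be underpowered. It does not supply the missing link. The protocol nowhere says that prolongation removes the apnea excess, that the cardiovascular gap applies to all complications, or what base rate and sidedness were used. An exploratory label does not excuse an unqualified 90% power statement attached to a named primary endpoint. Nor is this a detail left to an analysis plan: the protocol itself fixes the effect size, power and sample size.

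**Conclusion.** The concern holds. The only effect size behind 93 (120) per group differs from the study's comparison in both contrast and endpoint, so the 90% power claim is unsupported for the stated question. This rests on the protocol's text alone and not on any assumed rate.

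The size of the consequence does depend on assumptions. For a 15-point reduction (two-sided 5%, pooled formula, equal groups), power runs from 88 / 94% at 93 / 120 per group with a 20% base to 54 / 65% with a 50% base. The claim could be about right if the true base is near 19% and the true reduction is 15 points; the protocol supports neither figure. It should be fixed because it affects how a null result is interpreted, and correcting it is cheap.

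**What to change.** In the Sample Size section and the matching Study Abstract entry:

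1. Remove the apnea-versus-normal difference as the effect size and withdraw the 90% power claim that rests on it. If the sponsor does mean that prolongation offsets the apnea excess, and that the gap applies to all complications, state and justify both assumptions.
2. State the actual contrast (prolonged versus day-of-surgery extubation within severe apnea), the all-complication endpoint, the assumed day-of-surgery complication rate, whether the difference is absolute, and the sidedness of the test.
3. Keep 240 patients and report the reduction detectable at 90% power over a range of base rates, using the figures in Steps 3 and 4. Note that the groups are not randomised and that an unequal split lowers power. Recomputing the sample size from a justified rate and smallest reduction of interest would be an equally valid alternative.
4. Describe the comparison as exploratory, in line with the title.

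The cost of the route that keeps 240 patients is rewording in two places, with no extra patients or procedures and no change to the analysis. The stated power becomes less favourable: the text would acknowledge that, with 120 per group, 90% power covers only reductions of about 14 to 20 points or more, depending on the base rate.

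### The 93 per group for 90% power does not follow from the only complication rate the protocol cites, and the inputs behind it are not stated

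*Protocol*

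**What the plan says.** The Sample Size section, repeated almost word for word in the Study Abstract, names postoperative complications as the primary endpoint and gives these figures:

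- Effect: the perioperative cardiovascular complication rate in severe sleep apnea "is 15% higher than in the normal population [8"].
- Error rates and software: "Using a power of 90% and a significance level of 5%, sample size estimation was performed using PASS, version 11 (NCSS, LLC").
- Result: "We need to recruit 93 patients per group".
- Enrolment: "Accounting for loss to follow-up, dropouts, and other factors, we plan to include 120 patients per group". The Abstract says at least 120.

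The only absolute complication rate in the document is in the Research Background: "the incidence of cardiovascular complications within 30 days after surgery in patients with severe sleep apnea was as high as 30.1% [8"]. It carries the same reference number as the 15%.

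The study itself compares two groups of patients who all have severe sleep apnea, divided by "whether extubation time is prolonged (by 1-2 days"). The outcome under Study Outcomes is "Incidence of short-term postoperative complications, graded using the Clavien-Dindo classification".

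**The concern.** A two-proportion sample size needs two rates, a sidedness and a test. The section gives none of the first two and names no test for the calculation. It also leaves open whether 15% means percentage points or a ratio, so the 93 cannot be checked from the text. A reader who turns to the one rate available, 30.1% from the same source, does not get 93 at 90% power.

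The 15% is also borrowed from a different comparison. It contrasts severe sleep apnea with the normal population for cardiovascular events, whereas this study contrasts two extubation timings for all short-term complications. Nothing in the protocol supports 15 points as the effect of extubation timing.

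If the stated power is too high, a null result could be read as evidence of no effect when the study had a substantial chance of missing a true 15-point reduction.

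**Working it through.** **Inputs.** Power 90%, significance level 5% and 93 and 120 per group come from the Sample Size section. The rate 30.1% comes from the Research Background. The chi-square test comes from Statistical Analysis Methods. Assumed, because not stated: equal groups, no confounder adjustment, and 15% read each way in turn. Results are shown two-sided and one-sided.

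**Formulas, per group**, with d = p1 − p2 and p̄ = (p1 + p2)/2:

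- Unpooled: n = (zα + zβ)² [p1(1−p1) + p2(1−p2)] / d²
- Pooled: n = {zα √[2p̄(1−p̄)] + zβ √[p1(1−p1) + p2(1−p2)]}² / d²

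Here zβ = 1.2816, and zα = 1.9600 two-sided or 1.6449 one-sided.

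**Attempt to reproduce 93 from 30.1% and a 15-point reduction (30.1% vs 15.1%).** The variance sum is 0.2104 + 0.1282 = 0.3386, and d² = 0.0225.

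- Two-sided, unpooled: 10.507 × 0.3386 / 0.0225 = 158.1
- Two-sided, pooled: (1.9600 × 0.5915 + 1.2816 × 0.5819)² / 0.0225 = 161.3
- One-sided, unpooled: 8.564 × 0.3386 / 0.0225 = 128.9
- One-sided, pooled: 131.3
- Two-sided, arcsine 159.2; continuity-corrected 174.4

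**Other readings at 90% power (unpooled / pooled).**

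| Rates | Two-sided | One-sided |
|---|---|---|
| 45.1% vs 30.1% (30.1% as the lower rate) | 213.9 / 217.1 | 174.3 / 176.7 |
| 30.1% vs 26.2% (relative: 30.1/1.15) | 2751 / 2755 | 2243 / 2245 |

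None of these gives 93.

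**What would give 93 at 90% power.** With a 15-point gap, the pooled formula returns 93.0 for 19% vs 4% two-sided and 92.5 for 22% vs 7% one-sided. Mirror-image rates near 100% also work. The protocol states no such rates. Starting from 30.1%, the other group would have to be at about 11% two-sided, a 19-point difference.

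**Highest upper rate that still gives 90% power with a 15-point gap** (pooled to unpooled, mirror-image rates ignored):

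| n per group | Two-sided | One-sided |
|---|---|---|
| 93 | 19.0–19.4% | 22.1–22.5% |
| 120 | 23.0–23.5% | 27.5–28.0% |

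The cited 30.1% is above all four limits.

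**Exact power of the uncorrected chi-square (z) test:**

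| Rates | n per group | Two-sided | One-sided |
|---|---|---|---|
| 30.1% vs 15.1% | 93 | 0.696 | 0.800 |
| 30.1% vs 15.1% | 120, no losses | 0.804 | 0.880 |
| 45.1% vs 30.1% | 93 | 0.568 | – |
| 45.1% vs 30.1% | 120, no losses | 0.680 | – |

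**Reduction from 30.1% detectable with 90% power, two-sided:** 18.7 to 19.0 points at 93, and 16.9 to 17.1 points at 120.

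**Allowance for losses.** Going from 93 to 120 corresponds to 1 − 93/120 = 22.5%. No rate is stated.

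**A possible origin of 93.** The rates 30% vs 15%, one-sided, at 80% power give 92.7 (unpooled). This match would contradict the stated 90% and does not show what was done.

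**The case against.** The strongest reply is that the protocol never says 30.1% went into the calculation. It stands in the Background as an upper figure for 30-day cardiovascular events in one cohort, while the endpoint here is all complications. Other rates do give 93 at 90% power, so an arithmetic slip is not proven, and the recalculated powers are only as good as the assumed 30.1%. That stands: every power figure above is conditional, and the claim is that 93 cannot be reproduced from the protocol's own figures, not that it is impossible.

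The endpoint mismatch does not rescue the 93, however. The Data Collection section counts cardiovascular events together with pulmonary infection, leak, bleeding and others. Within the cited population, the all-complication rate cannot be below the cardiovascular rate. A higher upper rate makes a 15-point gap harder to detect up to mid-range: the pooled two-sided n is 202.8 at 40% vs 25% and 226.2 at 50% vs 35%. This study's patients may have lower risk than that cohort, since uncontrolled cardiovascular disease is excluded, but then the lower rate has to be stated and sourced.

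Two smaller points also have weight. The 70% figure applies only if 27 per group are lost and the test is two-sided, and losses before a short-term inpatient outcome may be fewer. The 22.5% need not be a planned dropout rate, since a 20% allowance gives 93/0.8 = 116.25, which could have been rounded up to 120.

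The study is also exploratory and observational. That makes the power less critical than in a confirmatory trial, but the protocol still makes an explicit 90% claim.

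**Conclusion.** The concern holds. The stated size and power are not supported by the protocol's own figures, and the inputs needed to check them are absent. If the rates are 30.1% and 15.1% with equal groups and no adjustment, power is about 70% two-sided (80% one-sided) at 93 evaluable per group. It is about 80% (88%) at 120 with nobody lost, so even full enrolment falls short of 90%. If 30.1% is the lower rate, two-sided power is about 57% and 68%. Separately, and whatever rates were used, the 15% is taken from another comparison and another endpoint.

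**What to change.** In both the Sample Size section and the Study Abstract:

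1. State what was entered in the software: both proportions, absolute or relative difference, sidedness, test and dropout rate.
2. Justify the two proportions for the actual contrast, all short-term postoperative complications under prolonged versus same-day extubation. If they differ from the 30.1% in the Background, cite their source and explain why.
3. Restate the power, or the difference detectable with 90% power, at 93 evaluable and 120 enrolled per group. If the base rate is in fact 30.1% and the test two-sided, that would be about 70% and 80% for a 15-point reduction, or detectable reductions of about 19 and 17 points.

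The cost is a wording change in two places once the software inputs have been retrieved, and probably a less favourable stated power. More patients are needed only if the sponsor chooses to keep 90% power at these rates.

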## **Study Flowchart**

Gastric cancer patients with severe sleep apnea

-> Apply Inclusion/Exclusion Criteria

-> Undergo surgical treatment

-> Decision on prolonging extubation time?

text

Yes -> Exposure Group: Prolonged extubation time

text

No -> Non-Exposure Group: Non-prolonged extubation time

Compare complication rates between the two groups

-> Follow-up for 1 year

-> Compare complication rates between the two groups

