### **Statistical Analysis Methods**

Chi-square test or Fisher's exact test will be used to compare categorical variables. Continuous variables will be expressed as median and IQR if non-normally distributed and analyzed using the Mann-Whitney U test, or as mean (SD) if normally distributed and analyzed using the t-test. Survival data will be analyzed using Kaplan-Meier curves. Enrollment is expected to be completed between June 2025 and June 2026. Follow-up is expected to be completed between June 2026 and June 2027.

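### The 1-year comparison of complication rates has only a yes/no test stated for it, which cannot properly handle patients who die or are lost complication-free before month 12

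*Protocol*

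**What the plan says.** The named outcome (Protocol, Study Outcomes) is the incidence of short-term complications by Clavien-Dindo grade. The section on follow-up also has complications assessed at visits from 1 to 12 months. The Study Flowchart places one comparison of complication rates straight after grouping. It then shows "Follow-up for 1 year" and repeats the same comparison.

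For such rates, Statistical Analysis Methods gives one rule: "Chi-square test or Fisher's exact test will be used to compare categorical variables". It also names Kaplan-Meier curves for survival data, but does not define that term or link it to complications. The Study Abstract's statistical methods do not mention Kaplan-Meier.

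Sample Size states "We need to recruit 93 patients per group" and then "Accounting for loss to follow-up, dropouts, and other factors, we plan to include 120 patients per group", 240 in all. No loss rate is given. Under Study Design, the groups follow from the anesthesiologist's perioperative assessment and not from randomisation.

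**The concern.** A chi-square or Fisher test at 1 year needs a yes or no for every patient in the denominator. A patient with a recorded complication poses no problem, since later loss does not undo the event. The difficulty is the patient who leaves complication-free, for example by death or loss at month 4. The test cannot censor, so two treatments remain:

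- **Drop the patient.** Patients who had a complication before leaving stay in, while those who left without one go, so the rate tends to be too high.
- **Count the patient as complication-free.** Any later complication is missed, so the rate tends to be too low.

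If loss and death were alike in both groups, much of this error would be shared. That cannot be taken for granted here. The groups are formed by clinical judgement, so they may differ in ways that affect both complications and retention. Enrolment ends in June 2026 and follow-up in June 2027, so nearly everyone has time to reach month 12. Missing 1-year status will therefore come mostly from death, withdrawal or loss, and in gastric cancer these may well be related to complications.

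**Working it through.** **Inputs.** From Sample Size: 93 needed and 120 enrolled per group. From the Research Background: 30.1%, a 30-day cardiovascular rate in severe sleep apnea and the only event rate in the protocol. It serves below as an assumed non-exposed complication rate. A 15-point lower rate in the exposed group is also an assumption.

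**1. The plan's own step.** (120 − 93)/120 = 27/120 = 22.5%, and 93/(1 − 0.225) = 120. The step is exact, but the 22.5% is back-calculated. The 93 itself is not reproduced from the stated inputs. For 30.1% against 15.1%, two-sided 5%, 90% power and pooled variance:

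n = [1.960·√(2·0.226·0.774) + 1.282·√(0.301·0.699 + 0.151·0.849)]² / 0.15² = 162 per group.

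That is a separate matter. Here 93 and 120 are taken as given.

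**2. The two treatments give different answers.** Suppose all 27 in each group leave complication-free and the 93 followed show 14 exposed and 28 non-exposed events.
- Dropped: 14/93 = 15.1% against 28/93 = 30.1%; difference −15.1 points, p = 0.014.
- Counted as complication-free: 14/120 = 11.7% against 28/120 = 23.3%; difference −11.7 points, p = 0.017.

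**3. Unequal loss.** Suppose both groups truly have 36/120 = 30.0% at 1 year. One group loses nobody. The other loses 27 complication-free patients, of whom 8 (about 30%) would later have had a complication. Counted as complication-free, that group shows 28/120 = 23.3%. A difference of 30.0 − 23.3 = 6.7 points appears where none exists.

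**4. Sensitivity to the unseen outcomes.** Start from 14/93 against 28/93 and let 8 of the 27 lost non-exposed patients have a complication, giving 36/120 = 30.0%.

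| Events in the 27 lost exposed | Exposed rate | p |
|---|---|---|
| 4 (15%) | 18/120 = 15.0% | 0.005 |
| 8 (30%) | 22/120 = 18.3% | 0.035 |
| 9 (33%) | 23/120 = 19.2% | 0.051 |

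**5. Extremes.** If every lost non-exposed patient and no lost exposed patient has a complication: 14/120 − 55/120 = −34.2 points. The reverse gives 41/120 − 28/120 = +10.8 points (p = 0.064).

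**6. Full cancellation.** The overall difference is (93/120)·d_followed + (27/120)·d_lost. Setting it to zero with d_followed = 15 points gives d_lost = 0.15 × 93/27 = 0.517, a gap of about 52 points in the opposite direction among the lost.

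**The case against.** The strongest reply is that rules for missing outcomes, censoring and analysis sets commonly belong in a statistical analysis plan, which is not shown. That stands for the absence of such rules. It does not dispose of the point, because the protocol itself draws a second rate comparison at 1 year and states only a yes/no test for a rate.

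A second reply is that Kaplan-Meier is named and could be meant for time to complication. The text does not exclude this. It does not say so either, and the flowchart speaks of comparing rates.

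A third is that the named outcome is short-term, so the 1-year comparison rests on one step of the flowchart. That is correct and limits the reach of the point.

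Two stronger readings are tempting but unsupported:

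- **A reader might infer that the plan discards known short-term outcomes,** because the sample size is enlarged for attrition. No section says that a patient lost at month 3 or 9 leaves the short-term comparison, and the flowchart makes that comparison before the year of follow-up.
- **A reader might infer that permitted loss exceeds the planned effect and so can decide the result.** The 27 are a recruitment margin that also covers unspecified other reasons, and the Study Abstract says at least 120. The 15% is described thus: "the incidence of perioperative cardiovascular complications in patients with severe sleep apnea undergoing non-cardiac surgery is 15% higher than in the normal population". That is not an effect of extubation timing, nor is it stated to be in absolute points. A loss percentage larger than an effect settles nothing in any case: what matters is how complication rates among the lost differ between groups.

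**Conclusion.** The point holds for the 1-year comparison only. The stated test has no proper place for patients who die or are lost complication-free before month 12, and the result can be biased if loss or death differs between the groups.

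The size depends on how many such patients there are and what happens to them. If the whole 22.5% margin were used, similar complication rates among the lost in both groups (9 and 8 of 27) would move an assumed 15.1-point observed difference from p = 0.014 to just above 0.05. Reversal is possible only towards the extreme, since full cancellation needs the 52-point opposite gap. With less loss the effect is smaller.

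These figures rest on assumed rates (30.1% borrowed from a cardiovascular 30-day outcome, and a 15-point reduction) and on reading the margin as event-free loss, which the protocol does not say.

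**What to change.** In Statistical Analysis Methods, state that the 1-year comparison:

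- uses the cumulative incidence of first complication from surgery to month 12, over all grouped patients;
- keeps every complication recorded before a patient is lost;
- censors event-free patients at last contact;
- treats death without a prior complication as a competing event;
- is accompanied by the number lost, and when, in each group.

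Keep chi-square or Fisher for the short-term comparison, and say that Kaplan-Meier refers to overall survival if that is what is meant.

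The cost is protocol wording and slightly more analysis. The visits at 1, 3, 6, 9 and 12 months are already planned, so no patients or procedures are added. Two limits remain. Late complications may be dated only to the interval between visits. Censoring still assumes that loss other than death is unrelated to the later risk of a complication, which is why loss should be reported by group. The change does not address confounding between the non-randomised groups.
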